4.1 Hypoxia-Inducible Factor Prolyl-Hydroxylase Inhibitors

Please see the vadadustat Investigator's Brochure for additional discussion and information for the following section.

Vadadustat is a synthetic, orally bioavailable, small molecule being developed as an inhibitor of hypoxia-inducible factor prolyl-hydroxylases (HIFPHs) for the treatment of anemia associated with CKD. Hypoxia-inducible factor prolyl-hydroxylase enzymes are also referred to as prolyl 4-hydroxylase domains (PHDs), of which the 2 most commonly expressed are PHD2 and PHD3. Vadadustat is a slightly more potent inhibitor of PHD3 (50% inhibitory concentration [IC₅₀] = 0.08 μM) than of PHD2 (IC₅₀ = 0.19 μM). The inhibition of PHD3 and PHD2 stabilizes hypoxia-inducible factor (HIF)-2α and HIF-1α, which in turn stimulates the production of EPO. In vivo animal efficacy and messenger ribonucleic acid (mRNA) data indicate that vadadustat induces the production of EPO from both renal and extra-renal sites (liver and brain), and this increase in EPO results in an increase in RBC production in the bone marrow. In clinical trials, vadadustat has been shown to facilitate iron homeostasis by decreasing hepcidin and increasing transferrin levels in healthy adult male volunteers and male and female CKD patients. This enables iron transport mechanisms that should enhance the terminal steps of erythropoiesis. Vadadustat offers the potential of flexible oral dosing that provides a more gradual and reliable means of titration than injectable hormones. Therefore, vadadustat is being developed as an alternative to the existing protein hormone ESAs.

4.2 Summary of Clinical Experience

Please see the vadadustat Investigator's Brochure for additional discussion and information for the following section.

To date, the safety, tolerability, pharmacokinetic (PK), and pharmacodynamic (PD) profiles of vadadustat have been characterized in 9 completed Phase 1 studies in healthy volunteers including 1 ethno-bridging study in Caucasian & Japanese subjects, 1 completed Phase 1 study in subjects undergoing chronic hemodialysis, 3 completed Phase 2a studies in NDD-CKD subjects, 1 completed Phase 2b study in NDD-CKD subjects, and 1 completed Phase 2 study in DD-CKD subjects. The Phase 2a studies evaluated Stages 3, 4, and 5 CKD (not on dialysis) subjects in a single-dose PK study, a multi-dose, 28-day, open-label, dose escalation pilot study, and a randomized, placebo-controlled study with 5 different dose groups dosed for 42 days. The

Phase 2b study evaluated Stages 3, 4, and 5 CKD (pre-dialysis) dosed for 20 weeks. The phase 2 study evaluated DD-CKD subjects on chronic hemodialysis dosed for 16 weeks. In the studies completed to date, a total of 548 subjects have received vadadustat, including 200 healthy volunteers and 348 subjects with CKD.

Vadadustat showed dose-dependent increases in EPO concentrations in Phase 1 and Phase 2a studies. The changes in EPO have been accompanied by an increase in reticulocytes as well as dose responsive increases in total iron binding capacity [TIBC] and decreases in hepcidin and ferritin. Overall, the safety profile for vadadustat has been acceptable and has supported further development. Vadadustat has demonstrated, dose proportional PK and dose-dependent PD (changes in serum EPO and/or Hb) in Phase 1 and Phase 2 studies covering the dose range of 80 mg to 1200 mg after single administration and 500 to 900 mg after repeated daily administration. The plasma half-life of vadadustat was about 4 – 5 hours, 7 – 8 hours, and 9 to 10 hours in healthy subjects, NDD-CKD patients, and DD-CKD patients, respectively.

Vadadustat is extensively metabolized. Vadadustat and its metabolites are eliminated from the body by dual routes of elimination, renal and fecal.

The urinary excretion of vadadustat and its metabolites has been shown to be less than 60% in healthy human volunteers. In a clinical study conducted to evaluate the effect of hemodialysis on the exposures to vadadustat, hemodialysis did not have an effect on the exposures of vadadustat or its metabolites. Given its short half-life and the dual routes of elimination, vadadustat is unlikely to accumulate in patients with CKD.

The completed Phase 2b, randomized, double-blind, placebo-controlled study to assess the hematologic PD response, safety, and tolerability of oral vadadustat for 20 weeks was performed in 210 subjects with anemia associated with NDD-CKD. Subjects were assigned to a study group based on their ESA status at Screening (naïve, previously treated, or actively treated) and were randomized 2:1 to receive either vadadustat at a starting dose of 450 mg/day or placebo. The dose of vadadustat was adjusted based on Hb levels and changes in Hb. Compared with the placebo group, the vadadustat-treated group demonstrated a significantly higher proportion of responders, defined as subjects achieving a Hb \geq 11.0 g/dL or an increase \geq 1.2 g/dL from baseline (54.9% versus 10.3%). Few vadadustat subjects exhibited Hb excursions $>$ 13.0 g/dL (4.0%), and favorable changes in iron mobilization and utilization were observed with treatment with vadadustat. The safety profile of vadadustat in this study supported further development.

Based on the Phase 1 and Phase 2 study results, vadadustat appears to be a suitable candidate for continued development as a treatment for anemia in patients with CKD.

4.3 Potential Benefits and Risks

Please see the vadadustat Investigator's Brochure for additional discussion and information for the following section.

Trials of injectable erythropoiesis-stimulating agents (ESAs) in patients with anemia secondary to NDD-CKD or DD-CKD have demonstrated an increased risk of cardiovascular events associated with higher Hb targets (Besarab 1998; Singh 2006; Pfeffer 2009). Post-hoc analyses performed by the FDA and others have shown an association between these adverse outcomes and supraphysiologic serum EPO levels and/or Hb oscillations and overshoots (McCullough 2013, Unger 2010). In studies to date, oral vadadustat daily increased mean Hb with few excursions above the target range. In addition, serum EPO levels remained well below those

reported with ESAs in the literature. As a result, there is the potential for the investigational drug vadadustat to provide an effective and safe therapeutic option for the treatment of renal anemia.

In addition, vadadustat may enhance iron metabolism and transport. Phase 1 and Phase 2 trials have demonstrated a consistent dose-dependent increase in TIBC and decrease in ferritin and hepcidin. Mechanistic studies have demonstrated that HIF stabilization downregulates the iron absorption regulator hepcidin, and upregulates the iron-mobilizing regulators ferroportin and transferrin (and its receptor) (Peyssonnaud et al. 2007). Potential clinical benefits include enhanced erythropoiesis and decreased exogenous iron requirements.

The toxicological profile of vadadustat supports continued development in the ongoing Phase 3 clinical trials. Dose-limiting toxicity noted in the exploratory toxicology studies was due to hemoglobinuric nephropathy (rat) and emesis associated with body weight loss (dog). Dose-limiting toxicity noted in the sub-chronic and chronic toxicology studies was due to exaggerated pharmacology and the sequelae of events related to polycythemia (increased RBC mass, blood hyperviscosity and fibrin thrombi); polycythemia-related toxicity was consistent across species, monitorable and reversible. In the completed clinical studies, vadadustat has had an acceptable safety profile to support further development.

5 STUDY OBJECTIVES AND ENDPOINTS

5.1 Primary Objective

The primary objective of this study is to demonstrate the efficacy and safety of vadadustat compared with darbepoetin alfa for the correction and maintenance of Hb in subjects with anemia secondary to NDD-CKD.

5.2 Primary Efficacy Endpoint

The primary endpoint used to assess the efficacy objective will be the mean change in Hb between Baseline (mean pretreatment Hb) and the primary evaluation period (mean Hb from Weeks 24-36).

5.3 Secondary Efficacy Endpoints

The key secondary efficacy endpoints include the following:

- Mean change in Hb value between Baseline (mean pretreatment Hb) and the secondary evaluation period (Weeks 40-52)
- Proportion of subjects with Hb values within the target range during the primary evaluation period (Weeks 24-36)
- Proportion of subjects with Hb values within the target range during the secondary evaluation period (Weeks 40-52)

Other secondary efficacy endpoints include:

- Proportion of time with Hb values within the target range during the primary evaluation period (Weeks 24-36)
- Proportion of time with Hb values within the target range during the secondary evaluation period (Weeks 40-52)
- Proportion of subjects with Hb increase of >1.0 g/dL from Baseline
- Time to achieve Hb increase of >1.0g/dL from Baseline

- Mean change in Hb between Baseline (mean pretreatment Hb) and the primary evaluation period (mean Hb from Weeks 24-36) stratified by pre-baseline ESA exposure
- Progression of CKD
- Proportion of subjects receiving IV iron therapy from Baseline to Week 52
- Mean monthly dose of IV elemental iron administered from Baseline to Week 52 in subjects who have received IV iron
- ESA rescue
- Dose adjustments from Baseline to Week 52
- Proportion of subjects receiving RBC transfusion(s) from Baseline to Week 52

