7.5.5.4 Procedures to Support Continued Study Participation

As part of the informed consent process, only subjects who fully understand and agree to full participation and long-term follow-up should be consented to participate. **It is important that subjects understand the long-term duration and purpose of a cardiovascular outcome trial and that the subject (or designee) continue to allow follow-up through global study completion which could be several years, even post subject's permanent discontinuation of study medication.**

In all cases of impending study medication discontinuation or subject request for stopping study visits, the Investigator will discuss with the subject their options of continuing in the study.

It is important to continue to follow every randomized subject, even if discontinued study medication, through global study completion at a frequency and approach that is agreed to between the Investigator and subject. Visit schedule and assessments are flexible and at the discretion of the Investigator and subject and will be clearly documented in the medical chart. Optimal data collection would include the following assessments through global study completion.

- EOS subject status (must collect at minimum)
- MACE Endpoint Questionnaire
- AE Assessment

The protocol allows flexibility of follow-up to maintain the subjects in active status post permanent discontinuation of study medication. For those subjects who decline full participation in the study post discontinuation of study medication, other options for continued follow-up on a subject include (but are not limited to):

1. Reduced frequency of on-site visits
2. Telephone visits in lieu of on-site visits
3. Telephone or any contact method (e.g., email, site staff visit subject's home, etc.) to verify vital status
4. Telephone or any contact method with an alternative person (family member or medical designee)

5. Study team access to medical records for reporting MACE data or vital status

In the most extreme case, the protocol will accommodate minimal contact with a subject or alternative method to obtain the subject's vital status. The objective is to **keep a subject's study status active** to ascertain at a minimum vital status (alive or deceased) at the global study completion.

The Investigator will ensure understanding and documentation of the reason(s) for a subject's desire to stop study procedures or stop study medication.

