8.4.3 Blinding

This will be an open-label study. Treatment assignment will be done through the IWR system and the Investigator, Sponsor, and CRO study teams will not be aware of which treatment will be assigned next. Treatments will be administered in an open-label fashion. The Sponsor and CRO study teams will be blinded to 'by treatment' aggregated analyses except for the unblinded statistician. In addition, the study will involve blinded adjudication of MACE, the use of an IDMC, and an identical schedule of visits, procedures, and assessments for both treatment groups in order to reduce the potential for bias. However, certain personnel directly involved in medical oversight of the study, regulatory reporting of safety information, and on-site monitoring activities may become unblinded to the treatment assignments of individual subjects during the course of the study.

The EAC will remain blinded throughout the full course of the study.

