8.4.6 Iron Supplementation

Investigators will prescribe iron supplementation during the study to maintain ferritin ≥ 100 ng/mL or TSAT $\geq 20\%$. In general, oral iron should be considered before initiating IV iron.

The use of iron-based phosphate binders (eg, ferric citrate) is permitted. For subjects who initiate dialysis, iron maintenance therapy via dialysate (eg, ferric pyrophosphate citrate) is also

permitted. However, the duration, dosage, and frequency of intradialytic iron should be documented in CRF.

Important: Because of the potential for oral iron to reduce the bioavailability of vadadustat, the study medication is not to be administered concurrently with an oral iron supplement (including multivitamins containing iron), iron containing phosphate binders, or any other medications containing iron. The subject should be instructed to take these medications at least 2 hours before or 2 hours after the dose of vadadustat.

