11 DATA ANALYSIS

Data collected throughout the study will be summarized using descriptive statistics and listed in by-subject listings. Continuous variables will be summarized using number of subjects with data, mean, standard deviation, median, minimum, and maximum. For categorical variables, the number and percentage of subjects in each category will be tabulated. Summaries will be provided by treatment group within appropriate analysis populations (as defined in [Section 11.2, Study Analysis Populations](#)) and by time point/time period as appropriate.

For Hb, Baseline will be calculated as the average of the central laboratory Hb measurements of samples taken at the screening visit closest to the date of randomization and the measurement taken at randomization.

For other parameters, unless otherwise specified, Baseline will be defined as the last available value prior to the first dose of study medication.

Hemoglobin values as assessed through the central laboratory will be used for efficacy and safety evaluations; local HemoCue Hb values will be used only for dose adjustments.

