11.6 Efficacy Analyses

The primary efficacy endpoint as well as all key and other secondary endpoints will be summarized using descriptive statistics by treatment group, as well as by study visit and/or analysis period as appropriate. Mean values of Hb as well as selected other efficacy parameters will be plotted across study visits/periods by treatment group.

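### The only IV iron dose endpoint is confined to IV iron recipients, a subset formed after randomization, so no randomized contrast of IV iron dose is named

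*Protocol*

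**What the plan says.** In the current protocol (Amendment 7, Version 8), Section 5.3 lists two IV iron endpoints among the other secondary efficacy endpoints: "Proportion of subjects receiving IV iron therapy from Baseline to Week 52" and, directly after it, "Mean monthly dose of IV elemental iron administered from Baseline to Week 52 in subjects who have received IV iron". The Synopsis words both the same way. No other endpoint in Sections 5.3 to 5.5 is an iron dose.

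Receipt of IV iron follows from prescribing during the trial. Section 8.4.6 has investigators give iron against ferritin and TSAT thresholds and adds: "In general, oral iron should be considered before initiating IV iron". Section 8.4.3 says "Treatments will be administered in an open-label fashion". Section 4.3 gives the sponsor's hypothesis: "Potential clinical benefits include enhanced erythropoiesis and decreased exogenous iron requirements".

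On analysis, Section 11.6 says that "all key and other secondary endpoints will be summarized using descriptive statistics by treatment group". Section 11.6.2 places secondary analyses in the randomized and full analysis populations by assigned treatment. That does not lift the restriction to recipients, which is part of the endpoint's definition.

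**The concern.** A comparison keeps the protection of randomization only if the groups compared are those that were randomized. IV iron recipients are selected later, by a route that treatment may alter and that investigators steer knowing the arm. If vadadustat spares the patients with the least need, those still treated have higher need. Their mean dose then rises although total IV iron use falls. If vadadustat brings in extra low-need patients, the reverse can happen.

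What is at stake is the reading of one secondary result. A reader of the dose row alone could draw the wrong conclusion about IV iron use, and the iron-sparing hypothesis in Section 4.3 has no dose contrast by assigned treatment to support or refute it.

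**Working it through.** The protocol states no rate, dose or power figure for IV iron, so there is no figure to reproduce.

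**Identity (no assumption).** In each arm, all-randomized mean = share treated × mean among recipients. Hence

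recipients-only ratio = all-randomized ratio ÷ share ratio (all vadadustat/control).

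**Size at assumed share ratios.** 1/0.90 = 1.11; 1/0.75 = 1.33; 1/0.50 = 2.00. If the share rises, say to a ratio of 1.25, the factor is 1/1.25 = 0.80.

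**Simple example (assumed).** Control: 20% treated, mean 100 mg/month, so 0.20 × 100 = 20. Vadadustat: 10% treated, mean 130, so 0.10 × 130 = 13. The recipient difference is +30; the all-randomized difference is −7.

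**Illustration at 925 per arm (protocol Section 11.1.1).** Assumed: control share 20%, recipient mean 100 mg/month, lognormal dose with CV 0.5 or 1.0.

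(a) The lowest-need fraction q of recipients is spared. With σ = √ln(1 + CV²) and k = Φ(σ − z_q), the recipient ratio is k/(1 − q) and the all-randomized ratio is k. The all-randomized variance per arm is p(s² + m²) − (pm)². Entries are difference ± 95% half-width.

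| CV | q | Share | Recipient mean | Recipient difference | All-randomized mean | All-randomized difference | Difference in share, points |
|---|---|---|---|---|---|---|---|
| 0.5 | 0.25 | 15% | 116.6 | +16.6 ± 10.6 | 17.49 | −2.5 ± 4.2 | −5.0 ± 3.5 |
| 0.5 | 0.50 | 10% | 136.3 | +36.3 ± 11.8 | 13.63 | −6.4 ± 4.1 | −10.0 ± 3.2 |
| 1.0 | 0.25 | 15% | 124.5 | +24.5 ± 22.6 | 18.68 | −1.3 ± 5.5 | −5.0 ± 3.5 |
| 1.0 | 0.50 | 10% | 159.5 | +59.5 ± 27.1 | 15.95 | −4.1 ± 5.5 | −10.0 ± 3.2 |

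(b) The same fractions are spared regardless of need. The recipient difference is 0. The all-randomized difference is −5.0 (half-width about 3.95 or 5.15 at CV 0.5 or 1.0) at a 15% share, and −10.0 (3.7 or 4.8) at 10%.

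(c) Every recipient needs 20% less and none is spared. The recipient difference is −20 (half-width 9.2 or 18.5). The all-randomized difference is −4.0 (3.8 or 5.0).

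So the two dose measures oppose each other in (a), only one moves in (b), and they agree in direction in (c).

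**Unrecorded time.** Follow-up after stopping drug is loose; Section 7.5.5.4 says "Visit schedule and assessments are flexible and at the discretion of the Investigator and subject". Assume equal iron rates before stopping, a fraction f of an arm stopping, recording that ends at month t of 12, and a rate after stopping of r times the earlier one. With u = (12 − t)/12, the true arm mean is proportional to 1 − f(1 − r)u. Counting unrecorded time as zero gives 1 − fu; a recorded-time denominator gives 1. For t = 8 or 4 and r from 0.5 to 2, the vadadustat/control ratio is off as follows.

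| Stopping, vadadustat v control | Unrecorded time as zero | Recorded-time denominator |
|---|---|---|
| 25% v 15% | −1.8% to −12.7% | −5.7% to +3.6% |
| 30% v 10% | −3.6% to −23.8% | −11.1% to +7.4% |

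Neither rule is clean.

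**The case against.** The strongest reply is that no wrong comparison is planned. The endpoint carries no test or margin, and the protocol commits only to descriptive summaries. The two adjacent endpoints form a standard two-part description, and a reader who sees both rows is not misled in any case above. Section 11 plans that "Continuous variables will be summarized using number of subjects with data, mean, standard deviation, median, minimum, and maximum", so share × recipient mean gives each arm's all-randomized mean, and even an unadjusted interval can be worked out. The proportion endpoint is also the more sensitive one where patients are spared: in (a) its interval excludes zero in all four cases, the all-randomized dose in one. In (c) the recipient mean excludes zero at both CVs, the all-randomized dose at one.

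All of that stands, and it limits the point to a modest improvement. It does not remove it. The recipient restriction is fixed in the protocol's definition, so it is not a detail left to the SAP. The dose contrast by assigned treatment has to be assembled by the reader.

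A reader might go further and infer that the endpoint works against vadadustat, or that reversal is likely. The documents do not support this. Section 4.3 speaks of a potential benefit only. It also reports falling ferritin and rising TIBC, while Section 8.4.6 prescribes against ferritin and TSAT, so the vadadustat share treated could rise as well as fall. Nor does the unrestricted weekly dose endpoint in the superseded protocol bound in the same file show that the current wording is an error.

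**Conclusion.** The point holds as a limited one. By-arm mean doses among IV iron recipients are not a randomized comparison, and no listed endpoint supplies a randomized dose contrast. The identity linking the two ratios is exact. The factors of 1.11, 1.33 and 2.00 rest on assumed share ratios, and the scenarios rest on assumed shares, doses and CVs, so the real direction and size are unknown. The recipient mean is a legitimate answer to a narrower question; it is not an error in itself. The endpoint is an other secondary one, and nothing here touches the primary or key secondary conclusions or the sample size.

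**What to change.** In Section 5.3 and the Synopsis, state the dose endpoint as mean monthly IV elemental iron from Baseline to Week 52 in all randomized subjects by assigned treatment, with zero for observed time without IV iron. Give the between-arm difference with a 95% confidence interval. Keep the recipients-only mean and the proportion receiving IV iron beside it as descriptive components. Do not count time without medication recording as zero use; state how it is handled and add a sensitivity analysis, since a recorded-time denominator itself depends on follow-up after randomization.

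The cost is wording in two places, one table and that sensitivity analysis, with no new data item. The downsides are zero-heavy data, less sensitivity than the proportion endpoint in some scenarios, incomplete recording after drug is stopped, and coverage of IV iron only, since oral iron comes first. Open-label prescribing remains a limitation.

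Separately, and not as support for this point: footnote [x] of Appendix A ends medication recording at the EOT visit, whereas Sections 8.5.1, 9.2.1 and 9.3.10 carry it on beyond that visit. These should be reconciled.
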